## 2. Specific aim(s)

**Aim 1:** An existing evidence-based toolkit intervention will be adapted and redesigned by a patient and provider team into an engaging, narrative graphic novel curriculum useful in substance abuse counseling. The proven behavioral interventions will be augmented with health education material focused on MAT and HIV risk reduction. Together, these materials will comprise the Health Education Toolkit. The Health Education Toolkit (**TK**) will employ a shared decision making model to encourage 1) increased recovery engagement by patients, and 2) patient engagement in deciding whether to initiate and adhere to MAT.

**Aim 2:** We will provide training and support to increase patient access to MAT for alcohol-related SUDs at a centrally located Federally Qualified Healthcare Center.

**Aim 3:** We will assess the feasibility and acceptability of the HET Toolkit to estimate whether exposure to the Toolkit (**TK**) can reduce substance use and increase engagement with MAT. We will conduct a three-month, randomized controlled trial of 50 patients with active alcohol SUDs enrolled in inpatient and outpatient treatment to obtain estimates of effect on the following exploratory hypotheses:

**Exploratory Hypothesis 1:** Patients randomized to the **TK** will participate in shared decision making conversations with their counselors at higher rates than patients randomized to treatment-as-usual sessions (**TAU**).

**Exploratory Hypothesis 2:** Patients randomized to the **TK** will report greater satisfaction and acceptability with their individual sessions than patients randomized to **TAU**.

**Exploratory Hypothesis 3:** Patients randomized to **TK** treatment sessions will demonstrate a) larger reductions in substance use (drug and alcohol) and b) increases in abstinence measured by urine-confirmed, self-reported days using over the 3-month follow-up compared to patients randomized to **TAU**.

**Exploratory Hypothesis 4:** Patients assigned to the **TK** condition will demonstrate improved ASI Alcohol Severity Scores relative to patients assigned to **TAU**.

**Exploratory Hypothesis 5:** Patients randomized to **TK** will attend more specialty substance abuse intervention and treatment sessions over the 3-month follow-up period than patients randomized to **TAU**.

**Exploratory Hypothesis 6:** Patients randomized to **TK** will initiate MAT for alcohol dependence at greater rates than patients randomized to **TAU**.

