## **6. Explain procedures that will involve the subject**

We will work with 31 counselors from 1 inpatient and 2 outpatient substance abuse treatment sites (note that one treatment site was able to enroll counselors but not clients prior to closing study recruitment). We will travel to the substance abuse treatment sites in order to present the study and recruit counselors. After presenting the study, we will obtain written informed consent for those counselors who are willing to participate in the study (the recruitment process for counselors is described in more detail in section 9 below). We then will randomly assign counselors to the toolkit (**TK**) or treatment-as-usual (**TAU**) group. Randomization will be *within-sites*, and ordered in matrices to ensure that the study conditions are evenly distributed within the treatment site. We will then screen and recruit clients who are attending individual treatment sessions with these counselors to participate in the study (recruitment process for clients is described in more detail in section 9 below). As part of their treatment experience, all patients who provide informed consent will continue to receive all other standard substance abuse treatment at the participating treatment sites.

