We will travel to the inpatient and outpatient substance abuse treatment sites in order to present the study and recruit counselor participants. After presenting the study, interested counselors can schedule a time with research staff to consent into the study. At this scheduled time, research staff will obtain written informed consent and will then administer an assessment battery as part of the Baseline Interview. Research staff will only work with treatment sites whose administrators agree that they will not impose any negative consequences on counselors who choose not to participate in the study. We then will randomly assign counselors to the toolkit (TK) or treatment-as-usual (TAU) group, and counselor participants will schedule a time to complete the initial training on their assigned condition. Counselors will be paid \$25 for measures completed at the Baseline Interview, \$75 for the initial training, \$25 for each of the 3 booster trainings, \$20 for each set of 5 fidelity checklists up to \$200, and \$25 for measures completed 6-months post Baseline Interview. Counselors can earn up to \$400 throughout the course of the study.

Client Recruitment

Immediately after a counselor completes training (either TK or TAU), we will work with the counselor to schedule a date within the next two weeks to present the study to patients who are on his or her caseload. On the scheduled day, research staff will travel to the treatment site and will present the study to those patients who attend individual therapy sessions with the counselor. Patients who are interested in the study will be asked to complete a brief verbal screening consent. We will administer the AUDIT; patients who score a 16 or above (criteria for moderate to severe alcohol use disorder) will receive further screening. We will then administer the MINI (modified for DSM-V criteria). Patients must meet criteria for current alcohol SUD (i.e., positively endorse at least 2 of the 11 items on the MINI) and have experienced 6 days of alcohol use in the past 60 days in order to be eligible. To maximize

generalizability and practical relevance of our findings, only patients who are unable to provide valid informed consent will be excluded. We expect to recruit 50 patients.

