## Data Analysis Plan

**Data Management and Analysis-** All interview and self-report measures will be completed via a web-based data entry program that has been used at TRI and the University of Pennsylvania for the past 5 years. Direct data entry reduces errors that can occur when transferring information from paper forms into electronic files. See our Data Management Plan for data integrity procedures. Prior to performing analyses, standard data screening/cleaning procedures will be applied: re-screening the data for data-entry errors, assessing the extent and pattern of missing data, and checking that appropriate assumptions of normality are met, employing remedial measures when necessary. We will check to confirm that the groups do not differ at baseline on relevant background variables using analyses of variance (ANOVA) for continuous variables and log-linear models for discrete or ordinal responses. The randomization process should minimize the need for the inclusion of covariates to reduce bias in the treatment comparisons. However, relevant covariates will be considered for inclusion in the analyses to improve the precision of estimation of the effects .

**Exploratory Hypothesis 1: Patients in the TK Condition will** participate in shared decision making conversations with their counselors at higher rates than patients randomized to **TAU**. Number of sessions in which patients indicate that their counselors conducted a shared-decision making conversation at the 6-week and 3-month follow-up will be examined. Average number of sessions per patient will be compared at the 6-weeks and 3-month follow-up point. We will calculate effect sizes between conditions using Cohen's d. Quality of shared decision making conversations will be calculated using a subscale of the fidelity checklist. Differences in patient perceived quality will be averaged, and effect sizes will be calculated using Cohen's d.

**Exploratory Hypothesis 2: Patients in the TK will report greater satisfaction and acceptability with their individual sessions than patients randomized to TAU.** Scores on the Patient Satisfaction measure will be averaged and compared between conditions for the assessment at the three-month follow-up point. We will calculate overall Satisfaction rating and Satisfaction with the Referred Services Subscale score. We will calculate effect sizes using Cohen's d.

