**Exploratory Hypothesis 3: Patients in the TK condition will demonstrate increased alcohol and drug abstinence (UA verified) and fewer days of self-reported alcohol and drug use during treatment and at follow-up than TAU patients.** We will compare rates of urinalysis-confirmed abstinence in the two groups at weeks 6 and 12.. The model will include terms for group, time, and their interaction, and baseline urine result along with any other necessary variables will be included as covariates. We will also compare days of self-reported alcohol and drug use based on the TLFB completed at the 6- and 12--week assessments. We will examine mean differences in abstinence rates and days of use, and estimate effect sizes using Cohen's d.

**Exploratory Hypothesis 4: Patients assigned to the TK condition will demonstrate improved ASI Alcohol Severity Scores relative to patients assigned to TAU.** We will calculate the ASI Alcohol Severity Score for patients in each condition, and examine change scores from baseline to 3-months. We will examine size of effect between condition change scores using Cohen's d.

**Exploratory Hypothesis 5: Patients assigned to the TK condition will demonstrate higher rates of engagement in substance abuse treatment than patients assigned to TAU.** Patients in the two groups will be compared on the number of treatment sessions attended in the past 90 days at the 3-month assessment. We will estimate size of effect differences on retention using Cohen's d.

**Exploratory Hypothesis 6: Patients assigned to the TK condition will demonstrate higher rates of Vivitrol initiation than patients assigned to TAU.** A logistic regression model will be used to compare patients in the two groups on initiation rates at the 3-month assessment. Patients will be considered MAT initiated if they receive a Vivitrol injection during the relevant time period, or if they attended an evaluation for Vivitrol and were deemed inappropriate for Vivitrol and referred to an alternative MAT.

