**Missing Data:** As recommended by Lavori , we will analyze the data under an intent-to-treat principle in which all patients initially randomized will be included. We will characterize the group of patients who drop out before the end of the study using logistic regression models to relate dropout to these characteristics. These characteristics will be drawn from the data gathered during the study. These analyses will allow us to determine whether the drop out process is completely at random. We cannot test whether the process is missing at random (i.e. drop-out independent of values of

missed responses, conditional on covariates and observed responses), but we will attempt to obtain information on the reason for drop out. The mixed effects models will accommodate some missing data and drop out. We will examine simple pattern mixture models to assess whether the longitudinal missing data are ignorable.

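### Counselors are randomized but the SAP analyses patients: H6 has no counselor effect, H3 does not specify one, and Cohen's d has no planned interval

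*SAP*

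**What the plan says.** **Who is randomized.** Protocol section 9 (Counselor Recruitment) says: "We then will randomly assign counselors to the toolkit (TK) or treatment-as-usual (TAU) group". Section 6 adds that this is done within site, "ordered in matrices to ensure that the study conditions are evenly distributed within the treatment site". Patients are recruited afterwards from the caseloads of those counselors, and being on such a caseload is inclusion criterion (a). Nothing in either document describes randomizing a patient.

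**How the hypotheses and the analysis set are worded.** Hypothesis 1 in Protocol section 2 says that toolkit patients "will participate in shared decision making conversations with their counselors at higher rates than patients randomized to treatment-as-usual sessions". The SAP repeats the phrase ("with their counselors at higher rates than patients randomized to" TAU), and its Missing Data paragraph says "we will analyze the data under an intent-to-treat principle in which all patients initially randomized will be included".

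**Planned analyses.**
- H6: "A logistic regression model will be used to compare patients in the two groups on initiation rates at the 3-month assessment". No counselor term or cluster-robust variance is named.
- H3: "The model will include terms for group, time, and their interaction, and baseline urine result along with any other necessary variables" are covered, the last group entering as covariates. No counselor term is named.
- Missing Data: "The mixed effects models will accommodate some missing data and drop out". The random effects are not given, nor are the hypotheses to which these models apply.
- H1 to H5: Cohen's d, without a standard error or interval.

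**Use of the results.** Protocol section 5 sets power aside and says the effect sizes will determine the sample size of a later, fully powered trial.

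**The concern.** Patients of one counselor share that counselor's skill, style and delivery of the sessions, and they always share an arm. If their outcomes are positively correlated, a patient-level analysis counts more independent information than the design supplies. Its standard errors are then too small and its intervals too narrow.

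The analyses are affected differently. H6 is a patient-level model as written. H3 is under-specified. The comparisons made only through Cohen's d involve no stated inference, so nothing there is computed wrongly. The gap is that no uncertainty is planned for a quantity intended to size another trial, and a patient-level interval added later could be too narrow.

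The wording matters too. Read literally, the intent-to-treat set is empty, because no patient is randomized. Read with Protocol sections 6 and 9, it can only mean patients of randomized counselors, and the SAP should say so.

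**Working it through.** The plan states no alpha, power, ICC, SD or target effect, so there is no figure of its own to reproduce. A two-sided 5% level is used below for illustration only.

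**Inputs from the documents**
- 50 patients, 25 per arm (Protocol sections 2, 4 and 9). Section 8 gives 350, which conflicts and is not used.
- 31 counselors (Protocol sections 4 and 6). One site supplied counselors but no patients (section 6), so fewer than 31 contribute.
- Booster trainings follow a counselor's first, third and fifth patient (Protocol section 6), so five patients per counselor is within the protocol's own planning.

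**Assumptions:** ICC 0.01, 0.10 and 0.20; two layouts; H6 initiation rates of 10%, 20% and 30%.

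**Formula.** Design effect DE = 1 + (m − 1) × ICC, with m patients per counselor. The true standard error is √DE times the patient-level one.

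**Layout A, all 31 counselors contribute**
- m = 50/31 = 1.61: DE = 1.006, 1.061, 1.123; standard errors 0.3%, 3.0%, 6.0% larger.
- Whole-number caseloads (19 counselors with 2 patients, 12 with 1): size-weighted mean (19 × 4 + 12 × 1)/50 = 1.76; standard errors 0.4%, 3.7%, 7.3% larger.

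**Layout B, 5 counselors per arm with 5 patients each**
- DE = 1 + 4 × ICC = 1.04, 1.40, 1.80; standard errors 2%, 18%, 34% larger.

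**Interval for d (at d = 0)**
- Patient-level: SE = √(2/25) = 0.283; half-width 2.011 × 0.283 = 0.569 (48 df).
- Layout B with site as a stratum: 10 counselors, two arms and two sites with patients leave 7 df, t = 2.365. Half-width = 2.365 × √(0.08 × DE) = 0.682, 0.791, 0.897.
- Ratios to 0.569: 1.20, 1.39, 1.58, that is 20%, 39% and 58% wider. At ICC 0.01 nearly all the widening comes from lost degrees of freedom.

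**H6, size of the patient-level Wald test.** Group-only logistic regression, 25 per arm, no true effect, beta-binomial counts within counselor. Reject if |log odds ratio / SE| > 1.96, with SE² the sum of the four reciprocal cell counts. Data sets with no finite estimate count as not rejected. Layout A (whole-number caseloads) is by exact enumeration. Layout B and the ICC 0 column are from 200,000 simulated trials, and exact enumeration agrees within 0.1 percentage point.

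| Initiation | ICC 0 | A: ICC 0.01 / 0.10 / 0.20 | B: ICC 0.01 / 0.10 / 0.20 |
|---|---|---|---|
| 10% | 0.5% | 0.5 / 0.7 / 0.9% | 0.6 / 1.6 / 2.8% |
| 20% | 3.3% | 3.4 / 4.0 / 4.6% | 3.6 / 6.7 / 10.1% |
| 30% | 4.7% | 4.7 / 5.5 / 6.3% | 5.0 / 9.2 / 13.8% |

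At 10% initiation in layout B, 14% to 29% of trials (ICC 0 to 0.20) give no finite estimate, almost always because an arm has no initiations.

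**H3.** No size was computed, because the model is not specified closely enough. As illustration only, a single-time-point patient-level t test of means in layout B has size of about 5%, 10% and 15% at the three ICCs (100,000 runs). The SAP plans no such test.

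**The case against.** **H3 is unspecified, not wrong.** A reader might infer that H3 omits the counselor. The documents do not support that: the open-ended covariate phrase and the reference to mixed models leave room for a counselor effect. The objection stands to this extent, that H3 standard errors may be too small, not that they are. But a patient random effect for the two visits, a natural reading of a mixed model here, would not correct for counselor. H6 has no comparable opening; the general SAP sentence on covariates concerns precision.

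**The effect may be negligible.** This stands for layout A, where H6 stays below 5% at 10% and 20% initiation and only slightly exceeds it at 30%. The layout B figures should not be quoted alone. Layout A is optimistic, however, since one site's counselors enrolled no patients.

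**Correlation is not shown.** The protocol describes what all toolkit counselors do, which argues for a difference between arms rather than between counselors within an arm. TAU counselors also cover medication facts, and initiation depends on clinic evaluation, medical eligibility and insurance. This stands: the claim is conditional on positive correlation. That is still a reason to plan for it, because the counselor conducts the sessions.

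**The study is exploratory, and recruitment was ended early.** No confirmatory claim is at risk. But the effect sizes are the stated product, and early closure removes neither the nesting nor the need for an interval.

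**Two further inferences are not supported.** Clustering does not by itself bias d. Recruiting patients after counselors were randomized and trained is a separate question, not assessed here.

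**Conclusion.** The point holds in a limited form and should be fixed.

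- **Wording:** the unit of randomization is misdescribed in Protocol section 2 and in the SAP, though Protocol sections 6 and 9 make the meaning recoverable.
- **H6:** the standard error is too small if outcomes correlate positively within counselor. The effect on test size runs from negligible (31 contributing counselors) to about 10% at 20% initiation and 14% at 30% (5 counselors per arm, ICC 0.20). At 10% initiation the size stays below 5% in both layouts, and non-estimability is the larger problem.
- **H3:** adjustment is not specified, and its consequence was not quantified.
- **Cohen's d:** the missing interval matters even with no clustering (half-width about 0.57). In the concentrated layout it is 0.68, 0.79 and 0.90 at ICC 0.01, 0.10 and 0.20.

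Confidence is high that these elements are missing. How much they matter depends on the assumed ICC and on how many counselors supplied patients, and the documents give neither.

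**What to change.** - State in Protocol section 2 and in the SAP that the counselor is the randomized unit, within site. Define intent-to-treat as all consented patients, analysed in the arm to which their counselor was randomized.
- H6: add a counselor random effect, or use GEE or a cluster-robust variance with a small-sample correction, with site as a stratum.
- H3: do the same, and also keep a patient-level effect for the two visits.
- State a fallback, for example a comparison of counselor-level means or proportions, for when the counselor variance is estimated as zero or an arm has no initiations.
- Report each d with a cluster-adjusted 95% interval, and report contributing counselors and patients per counselor by arm. An ICC may be given descriptively with its interval, noting that it will be very imprecise.

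**Cost:** wording, a little analysis work, and keeping counselor identity in the analysis file. No new patient assessments are needed. Intervals become wider, by the 20% to 58% shown above if only five counselors per arm contribute, and by much less if most of the 31 do.

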Addiction Severity Index-6th Edition Modified Version (ASI6-Modified): The ASI is a multi-dimensional interview used to measure the substance use, health, and social problems of those with alcohol and other drug problems, both at admission to treatment and subsequently at follow-up contacts (McLellan et al., 1992; McLellan et al., 1980). We are using an abbreviated version of the ASI-6 that eliminates many of

the items that do not contribute to our primary hypotheses and takes approximately 20 minutes to complete. We will use only the ASI domains for medical, drug use, alcohol use, and psychological status for covariate analysis. The ASI-6 produces *Recent Status Scores* in each of these four areas, which have demonstrated high levels of inter-rater, test-retest, and concurrent reliability (Cacciola et al., 2011). Our modified version also includes items from the QDS (see above) in order to obtain consistent and reliable estimates of alcohol use. *Administered at BL, 3 months, and 6 months.*

**EQ-5D-5L:** The EQ-5D™, a trade mark of the EuroQol Group, is a standardized measure of health outcomes. It takes only a few minutes to complete, and it provides a simple descriptive profile and a single index value for health status. *Administered at BL, 6 weeks, 3 months, 6 months.*

**Client Shared Decision Making Questionnaire:** The Shared Decision Making Questionnaire (SDM-Q client version; Kriston et al., 2010) is a validated 9-item questionnaire that measures the process of shared decision making between clinicians and patients. We adapted this measure to apply to substance abuse treatment decision making. This version of the questionnaire measures shared decision making from the patient's perspective. *Administered at BL, 6 weeks, 3 months, 6 months.*

**Client Satisfaction Questionnaire:** The Client Satisfaction Questionnaire was developed for this study and assesses the extent to which participants perceived the intervention to be helpful and useful. It contains both closed- and open-ended questions in order to obtain information that will help us further refine the intervention for dissemination. *Administered at 3 months only.*

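### The SAP says every randomized patient will be included, but H1, H2, H4 and H5 are specified only as Cohen's d on whatever values are available

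*SAP*

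**What the plan says.** The Missing Data paragraph of the SAP makes two promises. On the analysis set: "we will analyze the data under an intent-to-treat principle in which all patients initially randomized will be included". On method: "The mixed effects models will accommodate some missing data and drop out". It adds dropout regressions and simple pattern mixture models as checks.

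The hypothesis paragraphs of the same plan specify the following.

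- **H1:** "Average number of sessions per patient will be compared at the 6-weeks and 3-month follow-up point", followed by Cohen's d.
- **H2:** "Scores on the Patient Satisfaction measure will be averaged and compared between conditions for the assessment at the three-month follow-up point", followed by Cohen's d. Protocol Section 7 gives the timing of the satisfaction questionnaire as "Administered at 3 months only".
- **H3:** a model with group, time and interaction for urine-confirmed abstinence, adjusted for the baseline urine result. It is not called a mixed model, and the paragraph closes with differences in means expressed as Cohen's d.
- **H4:** "examine change scores from baseline to 3-months", then "We will examine size of effect between condition change scores using Cohen's d". Protocol Section 7 gives the ASI schedule as "Administered at BL, 3 months, and 6 months", so there is no 6-week ASI.
- **H5:** a count of sessions over the preceding 90 days, taken at the 3-month visit, then Cohen's d.
- **H6:** a logistic regression of initiation at 3 months.

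Protocol Section 5 declares power not relevant and says the estimated effect sizes will set the sample size of a later, fully powered trial.

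**The concern.** The Missing Data paragraph describes a property that the analyses for H1, H2, H4 and H5 have no means of delivering. A mean or a change score cannot be formed for a patient whose value is missing, and no imputation or other rule is given. A reader of the results would be told that everyone is included when the d values describe only those who were assessed.

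The d values are the main quantitative product of this trial and are to be carried into the design of the next one. If the patients who miss an assessment differ from those who attend, and do so differently in the two arms, the shift is carried forward with them. No confirmatory test is at risk, because every hypothesis is labelled exploratory.

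**Working it through.** **1. Promise against specification.** The documents give no dropout rate, effect size or precision target, so there is no planned figure to reproduce. The check is whether each analysis can keep a patient who misses an assessment.

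| Hypothesis | Measured when | Method stated | Patient without the 3-month value |
|---|---|---|---|
| H1 | 6 weeks, 3 months | mean per visit, d | counted at 6 weeks only |
| H2 | 3 months | mean, d | omitted |
| H3 | baseline, 6 weeks, 3 months | model for abstinence, then d on means | kept in the model if seen at 6 weeks; omitted from the 3-month d |
| H4 | baseline, 3 months | change score, d | omitted |
| H5 | 90-day count at 3 months | mean, d | omitted |

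The SAP's other provisions do not fill the gap. Screening missing-data patterns and modelling dropout describe the loss. Pattern mixture checks need a longitudinal model to act on. Covariate adjustment does not supply a missing outcome.

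**2. Possible bias.** Let m be the fraction missing in an arm and g the observed mean minus the missing mean, in SD units. The available-case difference departs from the all-patient difference by

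shift = m_TK × g_TK − m_TAU × g_TAU.

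All inputs here are assumptions.

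- 10% v 30% missing, g = 0.5 in both arms: 0.10 × 0.5 − 0.30 × 0.5 = −0.10.
- 10% v 30% missing, g = 1.0 in both arms: 0.10 − 0.30 = −0.20.
- 30% missing in each arm, same g: 0.
- 30% missing in each arm, g = 0.5 in TK only: 0.30 × 0.5 = 0.15.

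**3. A dropout model.** Assume no true effect and a 6-week to 3-month correlation of 0.6. Let the probability of missing the 3-month visit be p(z) = expit(a + 0.8z), where z is the standardized 6-week value. The expected observed 3-month mean is 0.6 × E[z(1 − p(z))] / (1 − m).

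- a = −2.22 gives m = 12% (3 of 25) and an observed mean of −0.054.
- a = −0.91 gives m = 31% (about 8 of 25) and an observed mean of −0.132.
- Difference: −0.054 − (−0.132) = 0.078 SD.

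Other dropout pairs under the same mechanism: 15% v 25% gives 0.041, 18% v 23% gives 0.021, and equal rates give 0. Using the 6-week value removes the shift, but here that is by construction, because dropout depends on nothing else.

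Equal rates protect only if the mechanism is also the same. In simulations with about 27% to 30% missing in each arm, but with the link to 6-week status differing by arm, the available-case d ran from 0.07 to 0.31. The top value needs the link to run in opposite directions in the two arms.

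**4. Scale against precision.** Near d = 0, SE(d) = √(2/n) with n per arm.

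- n = 25: √(2/25) = 0.283, 95% half-width 1.96 × 0.283 = 0.55.
- n = 20 (20% missing): √(2/20) = 0.316, half-width 0.62.
- n = 15 (40% missing): √(2/15) = 0.365, half-width 0.72.

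The loss of precision comes from the missing data, not from the choice of analysis. With 20% missing, using a 6-week value correlated 0.6 recovers only part of it: √[(2/20)(1 − 0.6² × 0.20)] = 0.305. The 0.078 shift is 0.078/0.283 = 28% of the full-sample SE.

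**The case against.** The strongest reply is that this is a feasibility study with no power claim, that the SAP never says it will restrict to completers, and that it leaves room for covariates. That is fair as to seriousness. It does not supply a rule for a missing value, and the inclusion statement is positive and unqualified.

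Four stronger readings are tempting, and the documents do not support them.

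- **That H5 implies unequal loss.** H5 predicts more treatment sessions under TK, and a reader might infer more missed research visits under TAU. Leaving treatment is not leaving follow-up. Protocol Section 6 provides for interviews of discharged patients elsewhere, with locator forms, repeated calls, mailings, public searches and $40 per follow-up interview. Only incarcerated participants are not pursued. Differential loss is possible but not predicted.
- **That a longitudinal model could help none of these outcomes.** This fits only H2, which is measured once. H1 has two follow-up points and H4 has a baseline ASI. The services questionnaire, a likely source for H5, is also given at 6 weeks.
- **That all four are completer analyses.** H1 is available-case at each visit, so a patient seen only at 6 weeks still counts there.
- **That intent-to-treat is abandoned.** Nothing suggests analysis other than by assigned arm. What is undelivered is the inclusion of everyone.

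The division between these four hypotheses and the rest is also not clean. H3 ends in d on mean differences, and H6 has no stated rule for unknown initiation status.

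**Conclusion.** The inconsistency stands on the SAP's own text. The inclusion of all patients and the reliance on mixed models are stated for the whole plan, but the analyses of H1, H2, H4 and H5 contain neither a mixed model nor a missing-value rule. H2, H4 and H5 lose anyone without the 3-month value.

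Bias is a possibility, not a finding. It needs loss that is related to outcome and that differs between arms in rate or mechanism. The figure of about 0.08 SD rests on assumed dropout of 12% v 31%, a slope of 0.8 and a correlation of 0.6. It falls to about zero with the same mechanism in both arms, and is well below the SE of 0.283. The plan should be corrected because it misdescribes who is in its estimates and because those estimates feed the next trial. It does not invalidate the study.

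**What to change.** 1. **H1 and H3:** take the 6-week and 3-month contrasts from a longitudinal model with group, time and interaction, plus the baseline value where one exists, in logistic form for abstinence. Standardize the contrasts and give 95% CIs. If baseline enters as a covariate, a patient with neither follow-up contributes nothing, so state the number used.
2. **H4 and H5:** use a baseline-adjusted contrast with a small imputation model: arm, site, baseline, and one or two 6-week variables already collected, such as drinking days from the Quick Drinking Screen and services from the NSMOS. A larger imputation model is likely to be unstable at 25 per arm.
3. **H2:** report the observed-mean d labelled as available-case, with n per arm. Any imputation would rest on proxies alone and belongs in a sensitivity analysis.
4. **Wording:** limit the inclusion statement to the analyses that deliver it. Label every observed-mean d as available-case, with n per arm and a 95% CI.

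No new data are needed. The cost is SAP wording, modest extra programming and some model dependence at this sample size.
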